4.2.3 Prior and concomitant medications

The frequency and percentage of participants reporting usage of prior medications, those reporting use of allowed concomitant medications, and those reporting usage of disallowed concomitant medications (refer to Section 6.5 of the CSP) will be summarized by treatment group and overall. Background medications will be summarized by treatment group and overall.

The summary tables will present data by generic term within ATC code.

The frequency and percentage of participants reporting usage of rescue medication will be summarized by treatment group and overall for scheduled visits.

4.2.4 Study treatments

Exposure to IP administration will be calculated in days as:

$$(last\ dose\ date\ of\ IP - first\ dose\ date\ of\ IP + 1)$$

where for 16-week placebo-controlled treatment period last dose date of IP will be the last dose date prior to entering the extension period, for the Week 52 end of study reporting the first and last dose date for the entire study will be used, and for the extension period alone the first dose date will be the first dose in the extension period.

Exposure will be summarized descriptively by treatment group for the safety analysis set.

The number and percentage of participants with duration of IP exposure in each of the following categories will also be summarized:

- <16 weeks
- ≥ 16 weeks and <24 weeks
- ≥ 24 weeks and <36 weeks
- ≥ 36 weeks and <52 weeks

IP exposure will be presented for the 16-week placebo-controlled treatment period, the 36-week extension period, and the overall Week 52 end of study reporting.

4.2.5 Compliance

Study treatment compliance with IP administration will be summarized descriptively by treatment group for the FAS and calculated as:

$$(Total\ doses\ administered / total\ doses\ expected) \times 100.$$

The total number of doses expected includes all visits with protocol scheduled IP administration on or before a participant's IP discontinuation or treatment completion date.

Compliance will be presented for the 16-week placebo-controlled treatment period, the 36-week extension period, and the overall Week 52 end of study reporting.

4.2.6 Primary outcome variable

4.2.6.1 Primary analysis

The primary endpoint is the proportion of participants with IGA 0/1 (ie, clear or almost clear) and a decrease in IGA of 2 or more points at Week 16, relative to baseline. The null hypothesis is: the proportion of participants on benralizumab 30 mg Q4W is equal to the proportion of participants on placebo. Whereas, the alternative hypothesis is: the proportion of participants on benralizumab 30 mg Q4W is not equal to the proportion of participants on placebo. That is,

H_0 : Difference in proportions (benralizumab 30 mg Q4W – placebo) = 0

H_1 : Difference in proportions (benralizumab 30 mg Q4W – placebo) \neq 0

Hypothesis testing for the primary analyses will be performed according to the multiple testing procedure described in Section 4.1.1.

For the primary and key secondary endpoints, the primary estimand will be based on the FAS (Section 2.2.2). Intercurrent events will consist of participants who withdraw from the study or require rescue therapy (defined in CSP Section 6.5.3). The primary estimand will regard these participants as non-responders from the time such events occur up to Week 16. A participant with missing data at a specific time point will also be considered as a non-responder at that time point.

The primary endpoint is a binary response that classifies a participant's skin clearance at Week 16 using the IGA score (see Section 3.2). Participants will be classified as responders if IGA 0/1 (ie, clear or almost clear) and they have a decrease in IGA of 2 or more points relative to baseline. Otherwise, participants will be classified as non-responders.

For the primary analysis, a logistic regression model will be fitted to the primary endpoint using a logit link function. The model will include treatment group and baseline covariates for age at screening (≥ 12 to < 18 years/ ≥ 18 years), blood eosinophils at screening (< 300 cells/ μ L; ≥ 300 cells/ μ L), and baseline IGA score. The strata variables will be used as recorded in the database, however for missing eosinophil data from the central laboratory the IVRS results will be used.

The model will be used to estimate the proportion of responders for benralizumab 30 mg Q4W and placebo, the difference between these proportions (benralizumab 30 mg Q4W – placebo) and an odds ratio, with corresponding 95% CIs. A p-value, corresponding to a 2-sided test, will be presented to compare the benralizumab 30 mg Q4W and placebo treatment groups. Marginal standardization methods (Bartlett 2018) will be used to calculate the proportions of responders, the difference in proportions and the confidence intervals from the model. Note

that if the logistic regression model does not converge to a solution due to low response rates in certain strata, these data will be analyzed using a Cochran–Mantel–Haenszel test.

The observed proportion of responders will be summarized using descriptive statistics by treatment group and each scheduled visit.

Sensitivity analyses to alternative missing data assumptions and alternative estimand approaches may be performed as described in Section 4.2.6.3 below.

4.2.6.2 Subgroup analyses for the primary outcome variable

To explore the uniformity of the detected overall treatment effect on the primary efficacy variable, subgroup analyses and statistical modelling including testing for interaction between treatment and covariates will be performed for the following factors:

- Region (Europe, North America, Rest of World)
- Gender (male, female)
- Age group categories (< 18 years, ≥ 18 – 35 years, ≥ 35 years) at screening from eCRF
- Age group categories (< 21 years, ≥ 21 – 35 years, ≥ 35 years) at screening from eCRF
- Blood eosinophils (< 300 cells/μL, ≥ 300 cells/μL) at screening from central laboratory results
- BMI ($\leq 30 \text{ kg/m}^2$, $> 30 \text{ kg/m}^2$)
- Race (White, Asian, Other)
- Duration of AD at enrolment (< median, ≥ median; calculated on FAS)
- Age at onset of AD (< 18 years, ≥ 18 years; if sufficient data: < 12 years, ≥12 – 18 years, ≥ 18 years)
- Baseline IGA score (3, ≥ 4)
- Baseline EASI (< median, ≥ median)
- Previous biologic use (yes, no; if sufficient data: responded to, failed, naïve) at screening from eCRF
- Previous immunosuppressant (yes, no; if sufficient data: responded to, failed, naïve) at screening from eCRF
- Co-morbid asthma (yes, no) at screening from eCRF
- IgE (< median, ≥ median) from central laboratory results; calculated on FAS
- Staph aureus (lesional) (yes, no)
- Staph aureus(non-lesional) (yes, no)
- Aeroallergens (yes, no) at screening from eCRF
- Food allergies (yes, no) at screening from eCRF

For each of the subgroup factors in turn, a separate logistic regression model will be fitted using the same model terms as used for the primary analysis (described in Section 4.2.6.1),

with additional terms for the subgroup main effect (unless the subgroup main effect is already included) and the treatment by subgroup interaction. If any model does not converge, respective sub-groups may be collapsed appropriately.

Similar outputs will be presented for each subgroup as for the primary analysis. The p-value for the interaction term by each treatment group will be presented in the analysis summary tables and forest plots will present the odds ratios with confidence intervals for each level of the subgroups.

It is important to note that the study has not been designed or powered to assess efficacy within any of these pre-defined subgroups (except for strata of age and eosinophils), and as such these analyses are considered as exploratory.

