1.2 Number of participants

Approximately 270 participants are expected to be enrolled/screened in order to achieve at least 160, and a maximum of 200, eligible study participants randomly assigned to study intervention to ensure that a broad distribution of participants is recruited across the range of ages and blood eosinophil levels to allow potential identification of responding subpopulations and appropriate cut-offs for future studies, if necessary.

Randomization will be stratified by blood eosinophils (< 300 cells/ μ L, ≥ 300 cells/ μ L) collected at screening and age at screening (≥ 12 to < 18 years and ≥ 18 years). Participants will be randomized in minimum cohort sizes across the baseline blood eosinophil and age subgroups; the intended distribution of participants in total across the treatment groups for each combination of these factors is summarized in Table 2. If the minimum recruitment target in any cohort is achieved, that cohort may remain open in order to fulfil minimum recruitment targets for the remaining cohorts. Thus, minimum recruitment targets may be exceeded in cohorts that remain open while fulfilling recruitment targets for other cohorts. Recruitment will stop when a maximum of 200 participants in total is achieved.

Table 2 Number of Participants Randomized by Stratification Factors

	Baseline blood eosinophils	
	<300 cells/ μ L	\geq 300 cells/ μ L
Adolescents (\geq 12 to < 18 years), n	20	30
Adults (\geq 18 years), n	40	70

For the primary analysis in the overall population, a minimum of 80 participants per treatment group will provide a high level of power (> 95%) to detect a 30% difference between benralizumab 30 mg Q4W and placebo for the primary endpoint. This calculation is based on a 2-sided test and a 5% significance level and assumes a response rate of 40% for benralizumab 30 mg Q4W and 10% for placebo.

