For subgroup analyses, a minimum of 35 participants per treatment group will provide at least 80% power to detect a 30% difference between benralizumab 30 mg Q4W and placebo (using the same assumptions as for the primary analysis). Thus, there is a high probability of detecting differences between treatments at the 2-sided 5% level in the baseline blood eosinophils \geq 300 cells/ μ L subgroup (with 50 participants per treatment) and in the adult subgroup (with 55 participants per treatment). In addition, there is a high chance of demonstrating statistical significance at the 2-sided 10% level in the adolescent subgroup (with 25 participants per treatment). Note that in the baseline blood eosinophils < 300 cells/ μ L subgroup, 30 participants per treatment group will provide an adequate amount of data to explore treatment differences, and will allow different cut-offs between ‘low’ and ‘high’ eosinophils at baseline to be assessed.

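### The SAP claims power for adults as one group, but its subgroup list has no ≥ 18 level, so no all-adult treatment effect is planned

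*SAP*

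**What the plan says.** Section 1.2 of the SAP: "Randomization will be stratified by blood eosinophils" at 300 cells/μL and by age at screening in two levels, ≥ 12 to < 18 and ≥ 18 years. Table 2 sets minimum cohort sizes for the four combinations. On those sizes the section claims a "high probability of detecting differences between treatments at the 2-sided 5% level" in the eosinophil ≥ 300 subgroup (50 per treatment) and "in the adult subgroup (with 55 participants per treatment"). For adolescents (25 per treatment) it makes a similar claim at the two-sided 10% level. It makes no power claim for eosinophils < 300.

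Section 4.2.6.1: "The model will include treatment group and baseline covariates for age at screening" (the two-level stratum), screening eosinophils and baseline IGA. There is no treatment-by-age term.

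Section 4.2.6.2 lists the subgroup factors. The first for age at screening is "Age group categories (< 18 years, ≥ 18 – 35 years, ≥ 35 years) at screening from eCRF". The second has the levels < 21, 21–35 and ≥ 35. Each factor gets its own model with a treatment-by-subgroup interaction, and the forest plots show an odds ratio for each level. On merging levels: "If any model does not converge, respective sub-groups may be collapsed appropriately". The section ends by saying that the study was not powered for these subgroups, "except for strata of age and eosinophils), and as such these analyses are considered as exploratory".

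**The concern.** The two sections do not meet. Section 1.2 justifies part of the sample size by what can be learned in adults as one group, and the closing sentence of Section 4.2.6.2 counts the age strata among the subgroups for which the study is powered. Yet the list that fixes what will be run splits adults at 35 in one factor. In the other it also puts adults aged 18 to 20 into the same level as adolescents.

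As written, a subgroup estimate for which the SAP says it has power, on a factor the trial randomises by, would not be produced. Nor would the direct adolescent-versus-adult interaction test. Section 1.2 says that recruitment across ages is meant to help identify responding subpopulations. If an all-adult estimate is then wanted, it would have to be defined after unblinding, when its prespecified status can be questioned.

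**Working it through.** **1. Match each power claim to a listed level**

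| Subgroup with a power claim (Section 1.2) | Size from Table 2 | Matching level in Section 4.2.6.2? |
|---|---|---|
| Eosinophils ≥ 300 | (30 + 70)/2 = 50 per treatment | Yes, at the randomisation cut |
| Adolescents | (20 + 30)/2 = 25 per treatment | Yes, < 18 in the first age factor |
| Adults | (40 + 70)/2 = 55 per treatment | No |

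The ≥ 18 level under age at onset of AD is no substitute. It is a different variable, since an adult participant may have had onset in childhood.

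**2. Look for another route to an adult estimate**

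- The primary model has age only as a main effect, so it yields one treatment odds ratio common to both age groups.
- Collapsing levels is optional and conditional on non-convergence.
- No contrast combining the 18–35 and ≥ 35 levels is specified.

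**3. Reproduce the SAP's power figures**

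Inputs from Section 1.2: p1 = 0.40, p2 = 0.10, two-sided test, equal groups at Week 16. Pooled-variance normal approximation, with n per treatment:

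power = Φ[(0.30·√n − z·√(2·0.25·0.75)) / √(0.40·0.60 + 0.10·0.90)]

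The two square-root constants are √0.375 = 0.6124 and √0.33 = 0.5745; z = 1.960 at 5% and 1.645 at 10%.

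- n = 80: 99.5% (SAP: > 95%). Agrees.
- n = 35: (1.775 − 1.200)/0.5745 = 1.00, so 84.1% (SAP: at least 80%). Agrees; Fisher's exact test gives 78.5%.
- Adults, n = 55: (2.225 − 1.200)/0.5745 = 1.78, so 96.3% (Fisher 94.8%).
- Eosinophils ≥ 300, n = 50: 94.6%.
- Adolescents, n = 25 at two-sided 10%: (1.500 − 1.007)/0.5745 = 0.86, so 80.5% (Fisher 73.3%).

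The adult power statement is therefore arithmetically sound. What is missing is the analysis to go with it.

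**4. What the listed adult levels offer instead**

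The SAP gives no adult age distribution, so the split at 35 is an assumption, shown as a range. Power per level uses the same formula at two-sided 5%.

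| Split at 35 | 110 adults: n per treatment | Power | 150 adults: n per treatment | Power |
|---|---|---|---|---|
| 50/50 | 27.5 and 27.5 | 74.2% each | 37.5 and 37.5 | 86.6% each |
| 40/60 | 22 and 33 | 64.1%, 81.9% | not computed | not computed |
| 30/70 | 16.5 and 38.5 | 51.3%, 87.5% | 22.5 and 52.5 | 65.1%, 95.5% |

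The 150 is the most favourable case: the maximum of 200 less the minimum of 50 adolescents. Section 1.2 uses 35 per treatment as its subgroup benchmark. For both adult levels to reach it, 2 × 2 × 35 = 140 adults divided exactly evenly would be needed, against the 110 minimum.

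**The case against.** The strongest reply is that this is a slip in a list. The closing sentence of Section 4.2.6.2 already counts the age strata among the predefined subgroups. The 18–35 and ≥ 35 levels together cover all adults and nobody else, so an adult effect could be obtained from the planned three-level model. The subgroup results are labelled exploratory and lie outside the testing hierarchy of Section 4.1.1. The SAP makes no power claim for the two adult levels, so low power there contradicts nothing. Section 1 also sends regional analyses to a separate plan, which is not at hand.

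Much of this stands. The consequence is small, the intent can be guessed, and the power range in step 4 describes what would be reported instead of an adult estimate; it is not an error in the SAP. But an adult effect that could be derived is not one that is planned: the SAP specifies neither the contrast nor the merged level. That the closing sentence refers to the age strata as powered subgroups makes the gap an internal inconsistency. A separate regional plan, whatever it contains, does not repair the list in this SAP.

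**Conclusion.** The point holds. Of the three subgroups with a power claim at a stated significance level, adults are the only one without a matching level in the analysis. As written, the SAP yields no all-adult treatment estimate and no two-level treatment-by-age interaction test. The estimate left out has about 96% power under the SAP's own assumptions (40% versus 10%, 55 per treatment, two-sided 5%, normal approximation). The levels that replace it have 51% to 88% at the minimum of 110 adults and 65% to 96% at 150, assuming splits at 35 between 30/70 and 50/50. The effect is confined to exploratory subgroup reporting; the primary and key secondary analyses do not depend on it.

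**What to change.** Add age at screening (≥ 12 to < 18 years, ≥ 18 years), the randomisation stratum, as a factor in Section 4.2.6.2. Define it as in the primary model, with its treatment-by-age interaction test and a forest-plot row for each level. Keep the two three-level age factors as exploratory detail. Section 1.2 can then stand unchanged, since its adult power statement is correct.

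The cost is one bullet, one more model and two forest-plot rows, with no new data. The age main effect is already in the primary model, so only the interaction term is new.

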4.2.9.11 Biomarkers

To explore the pharmacodynamic effect of benralizumab, summaries and plots of absolute levels and changes from baseline in pharmacodynamic biomarkers including CCI

will be produced as appropriate.

To evaluate the association of baseline biomarkers with clinical efficacy, and assess for any markers potentially predictive of benralizumab treatment effect the following analysis techniques may be considered:

- Forest plots for binary efficacy measures (primarily IGA response, EASI-75 response may also be included if necessary) at Week 16 of odds ratio by biomarker quartiles or clinically relevant thresholds pre-defined before unblinding;
- Scatterplots of baseline biomarker levels versus continuous efficacy measures (change from baseline for EASI, POEM and SCORAD) at Week 16, with locally weighted smoothing (LOESS) lines by treatment as appropriate;
- If appropriate, forest plots presenting subgroup analyses of continuous efficacy measures at Week 16 (eg change from baseline for EASI) by subgroups defined by baseline biomarker levels. Groupings of baseline biomarker levels may include splitting biomarkers at the median, at tertiles, or at quartiles, or other clinically relevant thresholds of interest to be pre-defined prior to unblinding. Results would be presented in forest plots of treatment effect (difference between benralizumab and placebo in change from baseline in EASI at Week 16) in each level of the biomarker subgroups.

Additional Biomarker analyses may be explored separately outside of this SAP.

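### The subgroup models' only non-convergence remedy, merging levels, cannot give the promised per-level estimates for the 15 factors that have two levels as written

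*SAP*

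**What the plan says.** SAP Section 4.2.6.2 takes the terms of the primary model and refits it for each factor "with additional terms for the subgroup main effect (unless the subgroup main effect is already included) and the treatment by subgroup interaction". It reports the interaction p-value, and "forest plots will present the odds ratios with confidence intervals for each level of the subgroups". If a fit fails, the rule is "If any model does not converge, respective sub-groups may be collapsed appropriately". No other fallback is named for these models. The Cochran-Mantel-Haenszel (CMH) fallback in Section 4.2.6.1 is written for the primary model, and Section 4.2.6.2 carries over that model's terms, not its fallback.

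Most of the 19 listed factors are binary. Three are binary by default with an optional finer split, for example "Previous biologic use (yes, no; if sufficient data: responded to, failed, naïve) at screening from eCRF".

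The section calls these analyses exploratory, but it exempts the age and eosinophil strata from its statement that the study was not designed or powered for subgroups. Section 1.2 gives the search for responding subpopulations as a reason for recruiting across ages and eosinophil levels.

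**The concern.** When a level of a factor has no placebo responders, the treatment-by-subgroup logistic model has no finite maximum likelihood estimate for that level. This is separation, and it is the usual reason for such a model to fail at low response rates.

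Merging levels does not solve it. With two levels, nothing is left to compare after merging. With three, the sparse level is absorbed into a neighbour. The SAP gives no merging order and no criterion, and which arm-by-level cells are empty is known only after unblinding, so the choice would be made with results in view. An empty placebo cell can also be where the observed effect looks largest, so the rule may hide a level that the trial set out to look at.

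**Working it through.** **The SAP's own figures.** Inputs from Section 1.2: 40% response on benralizumab, 10% on placebo, 2-sided 5%. The pooled normal approximation gives power of 99.5% at 80 per arm (SAP: above 95%) and 84.1% at 35 per arm (SAP: at least 80%). Both are reproduced.

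**Count of factors in Section 4.2.6.2.**

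| Type | Factors | Number |
|---|---|---|
| Three levels | region, two age groupings, race | 4 |
| Always two levels | gender, eosinophils, BMI, AD duration, baseline IGA, baseline EASI, asthma, IgE, lesional and non-lesional Staph aureus, aeroallergens, food allergies | 12 |
| Two by default, three if data suffice | age at onset, previous biologic, previous immunosuppressant | 3 |

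Total 4 + 12 + 3 = 19; two-level as written 12 + 3 = 15.

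**Chance of an empty placebo responder cell.** With n placebo participants in a level and response rate p, P(none) = (1 − p)^n. The level sizes are those in Section 1.2.

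| Level | n | p = 10% (SAP) | p = 5% (assumed) | p = 15% (assumed) |
|---|---|---|---|---|
| Adolescents | 25 | 7.2% | 27.7% | 1.7% |
| < 300 cells/μL | 30 | 4.2% | 21.5% | 0.8% |
| ≥ 300 cells/μL | 50 | 0.5% | 7.7% | 0.03% |
| Adults | 55 | 0.3% | 6.0% | 0.01% |

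For the other factors the SAP gives no level sizes. A median split (about 40 per arm) gives 0.9^40 = 1.5% per level. A level holding 20% of an arm of 80 (n = 16) gives 0.9^16 = 18.5%.

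**Across the 15 two-level factors.** The trial was simulated with independent factors, 40% response on benralizumab, and a model counted as separated if any arm-by-level cell had no responders or no non-responders. Prevalences, independence and the 15% placebo rate are assumptions.

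| Per arm | Placebo rate | Prevalences | Trials with ≥ 1 separated model |
|---|---|---|---|
| 80 | 10% | 20–50% | 55–59% (mean 1.1 to 1.3 of 15 models, median 1) |
| 80 | 10% | all 50% | 24% |
| 100 | 10% | 20–50% | about 41% |
| 80 | 15% | 20–50% | about 27% |
| 80 | 15% | all 50% | 4% |

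The range 55–59% is the spread between separate runs with slightly different prevalence grids.

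**What happens when it occurs.** Constructed example: one level with 0/20 placebo and 8/20 benralizumab responders, the other with 6/60 and 24/60. The interaction coefficient was 7.0 after 8 iterations, 21.1 after 25 and 24.6 after 100, still not converged, with a standard error near 144,000. Merging the two levels gives 6/80 against 32/80, odds ratio (32 × 74)/(6 × 48) = 8.2, which is simply the overall effect.

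A Firth fit without covariates amounts here to adding 0.5 to each cell. For the sparse level:
- odds ratio = (8.5 × 20.5)/(0.5 × 12.5) = 27.9;
- standard error of the log odds ratio = √(1/8.5 + 1/20.5 + 1/0.5 + 1/12.5) = 1.50;
- Wald 95% interval about 1.5 to 526.

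The level stays reportable, and the interval shows how little it carries.

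**The case against.** The strongest reply is that little depends on this. The analyses are exploratory, the trial is Phase 2, and no hypothesis in the testing hierarchy is touched. The SAP permits merging but does not require it, and it promises outputs similar to the primary analysis, which include observed proportions, so an empty cell could still be shown descriptively. At 10% placebo response separation is not widespread: typically one model of 15, and fewer if the trial reaches its maximum of 200. Some of the 15 factors are plausibly correlated, so independence is only a convenience. And an interval from 1.5 to 526 identifies no responding subgroup. All of this stands and limits the weight. It does not supply a fallback for a two-level factor.

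A reader might infer more than the document supports:

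- **That merging is impossible for all 15 without exception.** Three of them have an optional three-level form that can fall back to two. With the four three-level factors, merging is workable in some form for 7 of 19.
- **That the adolescent level disappears.** Section 4.2.6.2 lists age in three bands, so adolescents would be merged with young adults; eosinophils is the exempted stratum that cannot be merged at all.
- **That the primary fallback is also defective**, since CMH applies "if the logistic regression model does not converge to a solution due to low response rates in certain strata". Table 1 asks for an odds ratio and a difference in proportions but does not require them to be model-based, and Mantel-Haenszel methods can supply both. The primary model has no interaction, and the chance of no responder among 80 placebo participants is 0.9^80 = 0.0002.
- **That the biomarker forest plots in Section 4.2.9.11 need the same change.** They are displays that may be considered, "of odds ratio by biomarker quartiles or clinically relevant thresholds pre-defined before unblinding", with no merging rule.

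**Conclusion.** The point holds as a minor one. The stated remedy cannot deliver the per-level odds ratios for the two-level factors, including eosinophils, and for three-level factors it loses the sparse level's estimate through an unspecified choice after unblinding.

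The figures of 7.2% (adolescents) and 4.2% (below 300 cells/μL) rest only on the SAP's 10% placebo rate and stated level sizes. The trial-wide 55 to 59% also rests on assumed prevalences and independence, and ranges from 4% to 59% over the scenarios at 10% or 15% placebo response. A 5% placebo rate would make the problem much commoner, but the SAP does not plan on it, so the conclusion does not depend on it. The primary result is not in question.

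**What to change.** Replace the merging sentence in Section 4.2.6.2 with:

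> If any treatment-by-subgroup cell has no responders or no non-responders, or the model does not converge, fit the same model by Firth penalised likelihood with profile-likelihood CIs, keeping all levels, and report responder counts by level and arm.

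The cost is this wording and one option in the SAS procedure; trial conduct does not change. The downsides are some shrinkage of odds ratios and wide intervals in sparse levels. Model-standardised proportions from such fits are also pulled toward 0.5, so show observed proportions for those levels. Leave the CMH fallback in Section 4.2.6.1 and the optional plots in Section 4.2.9.11 as they are.
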